1.1 Research reference numbers

Sponsor's Reference number: RHM MED2094

REC Reference: 23/NW/0060

SRB Reference number: RHM SRB0044

HTA Licence number: 12009

ERGO submission ID: 101633

ISRCTN: 16512683

1.2 Protocol version number and date

1.1 16th May 2025

1.3 Sponsor

University Hospital Southampton NHS Foundation Trust

Title	Comparison of the performance of 3 Host Immune response tests for distinguishing bacterial and viral acute respiratory infection (CHIRP study).		
Short Title	Performance of 3 host response tests		
Design	Observational, retrospective, diagnostic accuracy study		
Participants	Adults ≥ 18 years old, presenting to ED or AMU with acute respiratory illness (ARI)		
Planned Sample Size	200 patients		
Planned Study Period	Recruitment period: Up to three years from data of ethical approval (10 th January 2025 - 10 th January 2028)		
	Objectives	Outcome Measures	
Кеу	To evaluate the diagnostic accuracy of 3 host response tests for bacterial and viral infection compared to the reference standard of clinical adjudication	Positive percentage agreement (PPA) negative percentage agreement (NPA), Positive Predictive Value (PPV), Negative Predictive Value (NPV), Overall accuracy, AUROC (all with 95% confidence intervals).	
Exploratory	To evaluate the equivalence of EDTA blood and PAXgene RNA blood on gene expression values for Cepheid HR test (in development)	Correlation, Spearman's Coefficient, Kappa statistic	

5 Funding and resources

FUNDERS	FINANCIAL AND NON-FINANCIAL SUPPORT
NIHR CRN	Clinical fellow (1.0 WTE for 6 months)
BRC MII theme (via CRF)	Research nurse and Laboratory technician for
	sample processing
[name] PI fund	For consumables (Paxgene blood tubes)

6 Role of trial sponsor

The Sponsor is University Hospital Southampton NHS Foundation Trust (UHS), which is the organisation that is taking legal responsibility for the trial.

7 Background

Patients presenting to emergency departments are frequently given antibiotics that they do not need

Around 80-90% of adults presenting to emergency departments (ED) with acute respiratory infection (ARI) are treated with antibiotics (1,2), however much of this is unnecessary as around half of episodes of ARI are caused by viruses (3,4). This unnecessary antibiotic use is directly harmful to patients, as 20% of patients experience adverse events including C.difficile infection (5), and also promotes the development of antimicrobial resistance (AMR). AMR is one of the most serious threats to human health and measures to combat it are a global priority (6).

Testing for the presence of viruses in ARI does not reduce antibiotic use

Meta-analyses of trials of rapid molecular testing for respiratory viruses in hospital inpatients and EDs have demonstrated improvements in patient care across a range of outcomes, including antiviral use and infection control measures (7-12). However, the impact on unnecessary antibiotic use has been minimal (10-12). Human factor research suggests this is because the identification of a virus does not rule out concurrent bacterial infection (13).

Single host-response biomarker tests are not able to distinguish bacterial and viral ARI

The blood host-response (HR) biomarkers C-reactive protein (CRP) and Procalcitonin (PCT) are both raised in bacterial compared to viral ARI but neither is sufficiently accurate to distinguish them with confidence (14). Although studies of CRP testing in primary care have demonstrated antibiotic reductions (15), evidence in secondary care is lacking where CRP is routinely used in the assessment of patients with ARI, in whom antibiotic overuse remains common (4,7,8). In addition, studies of PCT have demonstrated that it is insensitive in detecting serious bacterial infection, including bacteraemia (16). Neither CRP nor PCT are widely used to guide antibiotic initiation in ARI in UK EDs.

The ongoing NIHR-funded PRONTO study (17) is evaluating the use of PCT combined with NEWS-2 score in EDs, in patients with suspected sepsis but does not specifically evaluate patients with ARI, where the underlying aetiology and risk-benefit of withholding antibiotics is different. The proposed PROTECT study is a platform study designed to evaluate multiple different diagnostics for infection but does not focus on AR (18).

Combination HR biomarker tests may be able to distinguish bacterial and viral ARI accurately and reduce unnecessary antibiotic use

Combination HR biomarker tests distinguish between viral and bacterial infections using separate immune response biomarkers for each, and have the potential to reduce unnecessary antibiotic use by reassuring clinicians and patients that bacterial infection is absent. There are currently two combination HR rapid tests that have UK regulatory approval, FebriDx and MeMed BV (19,20).

FebriDx (Lumos diagnostics, Carlsbad, US) is a point-of-care test (POCT) that detects 2 host immune response proteins, one raised with bacterial infection (CRP) and one raised in viral infection (Myxovirus resistance protein A) in a finger-pick blood sample. It is an instrument-free, immunochromatographic, lateral flow-based test with results in 10 minutes. The read-out is the presence or absence of 3 coloured lines assessed by visual inspection, with suggested interpretation provided by the manufacturer, figure 1a (19).

MeMed BV (MeMed, Tirat Carmel, Israel) detects 3 host immune response proteins; CRP, Interferon gammainduced protein 10 (raised in viral infection) and TNF-related apoptosis-inducing ligand (raised in viral and reduced in bacterial infection). The levels of these 3 proteins are computationally integrated into a score. The test uses an analyser (MedMed Key, a small-footprint immunoassay platform) that can be located at the point-of-care. Blood samples are loaded into a cartridge which is inserted into the analyser with results in 15 minutes. The read-out is a score from 0-100, divided into bands which indicate the likelihood of a bacterial or viral infection, based on pre-set cut-off values, figure 1b (20,21).

An alternative approach to detecting host immune response proteins testing is the detection of host mRNA (i.e. transcriptomic) to differentiate bacterial from viral infection. The TriVerity Acute Infection and Sepsis Test (Inflammatix, Sunnyvale, CA, USA), uses an isothermal reverse-transcribed loop-mediated amplification (qRT-LAMP) assay to measure levels of 29 host mRNAs in blood and incorporates machine learning to calculate 3 separate scores predicting the likelihood of bacterial infection, viral infection and illness severity. This 29 gene set classifier has shown good levels of accuracy at distinguishing bacterial and viral infection across a range of clinical infection syndromes. The test is not yet FDA approved or CE marked but this is expected early in 2025.

Why is this research important?

ARI is the commonest reason for antibiotic use in ED and around half of this is unnecessary. Antibiotics are very frequently prescribed to patients presenting to the ED with ARI (1) but around half of these prescriptions are thought to be inappropriate (24) with adults being more likely to be prescribed inappropriate antibiotics than children (25). Recent UK trial data suggest that 80-90% of adult patient presenting with unselected ARI receive antibiotics in ED (7,8).

Unnecessary antibiotic use is driven by aetiological uncertainty

Diagnostic uncertainty regarding the aetiology of ARI has been found to play major role in this (26) and in particular the inability to rule out a bacterial infection in the rapid timeframe required in EDs (13,1). In addition, previous studies have shown that provision of antibiotic prescriptions may be associated with increased patient satisfaction for ED visits for ARI (27) and that ED physicians are more likely to prescribe antibiotics if they perceive that patients want them (28).

AMR is driven by unnecessary antibiotic use and is a global threat

Bacterial resistance develops in response to selective pressure associated with all antibiotic prescribing but is accelerated by inappropriate use (29). A substantial increase in global rates of infections caused by resistant pathogens, in combination with limited new antimicrobial agents in development, has raised concerns of an impending 'post-antibiotic era' with catastrophic consequences for human health (6,30). AMR is now recognised as one of the biggest threats to global health and efforts to preserve the effectiveness of antibiotics through antibiotic stewardship are a priority (5,30).

Diagnostic tests are urgently needed to direct antimicrobials and facilitate stewardship

The need for new diagnostics to help combat AMR has been recognised and the development and assessment of rapid tests that distinguish between bacterial and viral infections have been listed as a priority by the WHO (31). The recently published UK department of health document 'Confronting antimicrobial resistance 2024 to 2029' lists the development and implementation of diagnostic tests

to guide antibiotic use as a key component of its action plan (32). The NIHR's stated aims are to support AMR research including the evaluation of diagnostics to guide antibiotic use

Balancing the risks and benefits of reducing unnecessary antibiotic use

Reducing unnecessary antibiotic uses in ARI needs to be balanced against the risk of undertreating clinically important bacterial infection. Currently used single HR biomarkers (CRP and PCT) lack sufficient accuracy to do this (14). Tests with improved accuracy are therefore needed and must be implemented within a robust and safe testing strategy.

EDs are a priority area for antibiotic stewardships

As the interface between the community EDs are a priority area for antimicrobial stewardship (1) and the impact of antibiotic overuse use in EDs extends far beyond these departments as prescriptions started in ED are usually continued in other departments when patient are admitted, or in the outpatient setting if discharged (1). The use of point-of-care testing in the ED setting could be a critical component of a strategy to reduce AMR (31).

Review of existing evidence

A systematic literature review of published research and trial databases was undertaken using terms related to single and combined HR biomarker tests in terms of diagnostic accuracy, usability and clinical impact. For single biomarker accuracy (CRP and PCT) a recent meta-analysis demonstrated the following levels of accuracy for diagnosing bacterial infection in ARI; CRP (cut off of >50mg/L), sensitivity of 74.9%, specificity of 74.6%; PCT (cut off of >0.1ng/L) sensitivity of 73.6%, specificity of 74%, compared to clinical adjudication (14).

Other than FebriDx and MeMed BV no other combined HR-POCTs with CE marking were found. Excluding studies related only to COVID-19, 5 diagnostic accuracy studies evaluating FebriDx and 6 evaluating MeMed BV were found with 1 recent systematic review and meta-analysis (33) that included all of these studies. 1 NICE MedTech briefing was found that evaluated FebriDx (34). Overall, these studies suggest that both FebriDx and MeMed BV may have improved diagnostic accuracy for diagnosing bacterial infection (~85-95% for both sensitivity and specificity) compared to single biomarker tests. However, all these studies were company sponsored or supported and were assessed as being at high risk of bias, plus estimates of accuracy were imprecise due to small numbers of patient in individual studies. Therefore, the level of certainty of evidence is considered low (33).

Three studies were found evaluating the accuracy of the RNA gene classifier used in the Inflammatix Triverity test, which all demonstrated similar levels of sensitivity and specific for bacterial and viral infection (34-36).

No studies were identified that evaluated the usability of any of the combined HR platforms in ED and only two studies evaluating impact were found (one each for MeMed BV and FebriDX) which were both small, performed in primary care and of very low methodological quality (37,38). No ongoing or planned non-industry studies were found evaluating either the usability or impact of FebriDx , MeMed BV or Triverity on antibiotic use in ED.

The current literature therefore provides a strong rationale for urgent independent studies of the currently available and emerging combined HR-POCTS to confirm company-supported data suggesting higher accuracy compared to single biomarker tests for ruling out bacterial infection, which could facilitate antibiotic stewardship.

Aim, objectives, and outcome measures

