7.1 Aims and objectives

To evaluate the diagnostic accuracy for the 2 commercially available combined HR-POCT platforms (MeMed BV and FebriDx) and for the Triverity test, for the diagnosis of bacterial and viral infection, against the reference standard of clinical adjudication.

Outcome measures

Key outcome measures:

Positive percentage agreement (PPA) negative percentage agreement (NPA), Positive Predictive Value (PPV), Negative Predictive Value (NPV), Overall accuracy, AUROC, all with 95% confidence intervals.

Exploratory outcome measures:

To evaluate the equivalence of EDTA blood and PAXgene RNA blood on gene expression values for the prototype Cepheid HR test (Xpert Bacterial vs. Viral assay).

Study design and methods

We will conduct a fully powered diagnostic accuracy study performed on samples prospectively collected from adults presenting with ARI (7) using the Southampton Research Biorepository (SRB) and including routinely collected clinical data including results of diagnostic testing for viruses and bacteria in addition to baseline clinical, laboratory and radiological data, and outcome data. The reference standard used by regulators for defining bacterial and viral infection is clinician adjudication (as no sufficiently accurate gold standard test exists) which take account of detailed clinical data including diagnostic tests for pathogens, blood test results (eg white cell count, PCT) radiological tests, and other data (37).

In accordance with guidelines, adjudication will be performed independently by three blinded experts, with a system for arbitration where there is discordance (37). Full methods for clinical adjudication are detailed in Tanner A, at al, Journal of Infection 2024 (38) Measures of diagnostic accuracy will be calculated for each HR test separately and compared.

Trial overview for patient-participants

Adult patients with acute respiratory illness in Southampton General Hospital's Emergency Department (ED) and Acute Medical unit (AMU) will be identified and assessed for eligibility for the trial. Potential participants would have been seen and assessed by the triage nurse or other triaging clinician but may not have been fully treated by their clinician. The triage nurse or other triage clinician may highlight potential participants to the study team. Potential participants will receive a participant information sheet, and be invited to ask questions, as part of the informed written consent process.

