7.3 Procedures for patient-participants

The following samples will be collected from all participants

- A combined nose and throat swab in viral transport media (x 2 as above)
- A finger-prick blood sample for immediate FebriDx testing (patients and clinical teams will be blinded to results as above)
- Venous blood sampling (EDTA, Serum and RNA Paxgene tubes, a total volume of not more than 16mls)

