9.2 Statistical analysis plan

Test results from the combined HR-POCTs will be compared to adjudicated aetiology using the different adjudication methods. Positive percentage agreement (PPA, used in place of sensitivity to reflect an imperfect reference standard), Negative percentage agreement (NPA, used in place of specificity to reflect an imperfect reference standard), positive predictive value (PPV), negative predictive value (NPV), and overall accuracy (with 95% confidence intervals), will be calculated for both bacterial (vs non-bacterial) and viral (vs non-viral) infection. ROC curves will be generated and AUC with 95%CI calculated. Performance metrics including AUROC will be compared between the tests using Chi Squared test and DeLong test.

10 Data management

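### The exploratory objective is equivalence of EDTA and PAXgene expression values, but no listed measure estimates the bias between tubes: correlation is blind to it and kappa sees only categorised calls

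*Protocol*

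**What the plan says.** The Protocol's study summary table gives the exploratory objective as "To evaluate the equivalence of EDTA blood and PAXgene RNA blood on gene expression values for Cepheid HR test (in development") and, in the cell beside it, the outcome measures "Correlation, Spearman's Coefficient, Kappa statistic".

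Section 7.1, under the exploratory outcome measures, repeats the objective ("To evaluate the equivalence of EDTA blood and PAXgene RNA blood on gene expression values for the prototype Cepheid HR test") and names no measure.

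Section 9.2 does not mention the tube comparison. Its comparative sentence, "Performance metrics including AUROC will be compared between the tests using Chi Squared test and DeLong test", concerns the diagnostic tests. The summary-table cell is therefore the only place in the Protocol that says how the tubes will be compared.

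The data are paired by design. Section 7.3 lists, for all participants, "Venous blood sampling (EDTA, Serum and RNA Paxgene tubes, a total volume of not more than 16mls").

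**The concern.** Equivalence of two specimen types on a continuous quantity means that the two give nearly the same value in the same patient. What most needs detecting is a systematic difference: one tube reads higher by a constant, or stretches or compresses the scale. Of the three listed measures, only the correlations act on continuous values, and they are built to ignore exactly those differences. Kappa measures agreement, but on categorised calls, whereas the objective names expression values.

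At stake is the reading of the exploratory result. A high coefficient set beside the word equivalence invites the conclusion that the tubes are interchangeable on expression values, when the bias between them has not been estimated. The risk is greatest for a proportional bias that leaves most calls unchanged, or where no cut-off has been fixed so that kappa is undefined or depends on the threshold chosen.

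**Working it through.** The Protocol gives no number of pairs, margin, alpha or power for this objective, so there is no figure to reproduce.

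**Step 1: exact result.** Let x be the PAXgene value, and let the EDTA value be y = a + b·y₀ with b > 0, where y₀ is the EDTA value free of systematic bias. Then:

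- Pearson: cov(x, y) = b·cov(x, y₀) and SD(y) = b·SD(y₀), so b cancels and a drops out.
- Spearman: the ranks of y are the ranks of y₀, so the coefficient is unchanged. This holds for any strictly increasing transformation.

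The Protocol does not name the type of its first-listed correlation; Pearson's is taken here.

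**Step 2: illustration.** The inputs are assumptions, not from the documents: true log₂ expression with SD 1 between patients, and independent error of SD 0.15 per tube. The run used 200 pairs (the planned sample size; the number of pairs to be run on the prototype is not stated) and 500 replicates. Kappa is taken at a cut-off at the reference median. The offset a is in between-patient SDs, with b = 1.

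| Offset a | Pearson | Spearman | Mean difference | Lin's concordance | Kappa |
|---|---|---|---|---|---|
| 0 | 0.978 | 0.974 | 0.00 | 0.98 | 0.87 |
| 0.25 | 0.978 | 0.974 | 0.25 | 0.95 | 0.79 |
| 0.5 | 0.978 | 0.974 | 0.50 | 0.87 | 0.62 |
| 1 | 0.978 | 0.974 | 1.00 | 0.65 | 0.32 |
| 2 | 0.978 | 0.974 | 2.00 | 0.33 | 0.05 |

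Limits of agreement are about ±0.41 around each mean difference.

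Closed-form checks:

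- Each tube's variance is 1 + 0.15² = 1.0225, so Pearson = 1/1.0225 = 0.978.
- Lin's concordance = 2/(2 × 1.0225 + a²). At a = 1 this is 2/3.045 = 0.66, and at a = 2 it is 2/6.045 = 0.33, matching the simulation to within 0.01.
- The SD of the difference is √(2 × 0.15²) = 0.212, and 1.96 × 0.212 = 0.416.

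**Step 3: proportional bias.** Set a = 0 and b = 0.5, so that one tube halves the spread. Pearson stays at 0.978, Spearman at 0.974, the mean difference at 0.00 and kappa at the median cut-off at 0.87. The limits of agreement widen to about ±1.03. Check: the variance of the difference is 0.25 + 0.25 × 0.0225 + 0.0225 = 0.278, its SD is 0.527, and 1.96 × 0.527 = 1.03. With the cut-off moved to 1.5 SD, the same data give kappa 0.04. Kappa's verdict on this bias therefore depends on a threshold that the Protocol does not state. The mean difference alone would also miss it, which is why limits of agreement or a concordance coefficient are needed as well.

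**Step 4: how far the size depends on the assumptions.** With error-to-patient SD ratio r, Pearson is 1/(1 + r²): 0.978 at r = 0.15, 0.80 at r = 0.5 and 0.50 at r = 1. That correlation lies close to 1 is a consequence of assuming little error. That it does not move with the offset is true at every r.

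**The case against.** The strongest reply is that the Protocol does not rely on correlation alone. Kappa is listed too, and it is a chance-corrected agreement measure. A reader might infer that the plan would pass the tubes as equivalent even if one of them moved every value past the assay's cut-off. The documents do not support that: the table above shows kappa falling from 0.87 to 0.05 as the offset grows, so with a cut-off in place the listed measures would expose such a shift. Nor is kappa's dependence on prevalence a strong complaint here, since section 9.1 expects about half of patients to have a bacterial aetiology. Both replies stand.

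It can also be said that the objective is exploratory, that the assay is a prototype, that the Protocol nowhere states that a high coefficient will be taken as proof of equivalence, and that a margin and detailed methods may sit in a statistical analysis plan that is not shown. These stand as well. They limit the weight of the point, and the absence of a margin is not itself the finding.

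What survives is a mismatch inside the Protocol. It names equivalence of values as the objective and then lists measures of which none estimates how far the values differ. Kappa does not close the gap, because it works on categories, needs a cut-off that the Protocol does not state, and can miss a proportional bias centred near that cut-off.

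**Conclusion.** The point holds in limited form. Correlation and Spearman's coefficient cannot show equivalence of EDTA and PAXgene expression values, and this is exact, resting on no assumed input. Kappa covers the categorical call but gives no estimate of bias in the values.

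The simulated sizes rest on the assumed SDs, cut-offs and 200 pairs, and are illustrations only. It would go too far to say that correlation is the Protocol's only measure, or that a shift across the cut-off would pass unseen. The real gap is bias in expression values that leaves calls largely unchanged, or any bias where no cut-off has been fixed. The consequence is confined to the exploratory objective; the key diagnostic-accuracy objective is not touched. The change is worth making because the named measures do not answer the named question and the repair is cheap.

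**What to change.** In the exploratory outcome cell of the study summary table, and to match in section 7.1:

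- Add the mean paired difference between tubes, on the log or cycle scale, with its confidence interval.
- Add Bland-Altman limits of agreement, or a concordance coefficient.
- Judge these against a margin set before the paired results are seen.
- Keep kappa, with percent agreement, for the categorical call, and state the cut-off used.
- Report correlation as descriptive only.

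Alternatively, keep the listed measures and reword the objective to association and call agreement rather than equivalence.

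A formal two one-sided tests procedure with Deming or Passing-Bablok regression for every gene would be more than an exploratory aim needs.

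The cost is a little more analysis and the work of choosing a margin. Both tubes are already drawn from every participant, so no new samples are required.
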